8.5.9 Reporting of unanticipated adverse device effects

The Investigator shall submit to the sponsor and to the reviewing IRB a report of any unanticipated adverse device effect occurring during the study as soon as possible (see US requirement 21 CFR 812:150 (a.), for contact details, see section 8.5.7.

8.5.10 Follow-up of unresolved events ongoing at termination of the study

All serious as well as non-serious AEs with a causal relationship to the study product or treatment procedure and ongoing at study end, shall be followed up after the subject's participation in the study is over. Such events shall be followed-up after the last study visit until resolved, assessed as chronic or stable, or subject is lost to follow up. Follow-up information shall be reported on the AE follow-up form.

8.5.11 Reporting and follow-up of events occurring after subject termination of the study

All Adverse Events with a causal relationship to the study products or treatment procedure that the Investigator becomes aware of, serious as well as non-serious, with onset after the study termination (subject's last study visit) shall be reported to the Sponsor by email to [contact]. The Investigator shall follow the subject until the event as resolved.

8.5.12 Pregnancy

Pregnancy itself is not regarded as an AE.

Effective

Version: 10.0

	Title 43USTT1904 CSP Infraorbital Hollows	Doc id MA-40833
--	---	---------------------------

If there is a pregnancy during the study period the subject must be withdrawn from any following study treatment, but should continue to be followed within the study and the outcome of pregnancy must be reported even if the delivery occurs after study completion.

A pregnancy confirmed during the study period must be reported by the Investigator on a pregnancy report form immediately upon acknowledge be submitted to the Sponsor according to contact details specified in section 8.5.7. The report can be prospective or retrospective. Follow-up shall be conducted to obtain outcome information on all prospective reports.

Cases that led to fetal distress, fetal death or a congenital abnormality or birth defect are to be regarded as SAEs and shall be reported on the exposure *in utero* report form to the Sponsor immediately but no later than 24 hours after the Investigators awareness. These events shall be handled as SAEs during data processing. Other complications during the pregnancy that are related to the pregnant woman and fulfils any serious criteria, such as pre-eclampsia requiring hospitalization, shall be reported and handled as SAEs. Elective abortions without complications shall not be reported as AEs.

8.5.13 Anticipated Adverse Events

Information regarding anticipated AEs for *Restylane-L* is included in the study specific IFU.

8.6 **Device deficiencies**

8.6.1 Definition of a device deficiency

A device deficiency is defined as an inadequacy of a medical device with respect to its identity, quality, durability, reliability, safety^{IV}, or performance.

Note: Device deficiencies include malfunctions, use errors, and inadequate labelling.

8.6.2 Recording instructions

When a device deficiency is discovered, Part A of the clinical study complaint form shall be completed by the Investigator. The type of complaint shall be described and injury to the subject or user or unintended exposure to study product shall be reported as applicable. If an injury has occurred, an AE or an SAE form shall be completed as applicable (refer to sections 8.5.5 and 8.5.7). If no SAE was experienced as a result of the device deficiency the Investigator shall assess whether or not the device deficiency could have led to an SAE if:

- Suitable action had not been taken,
- Intervention had not been made or,
- Circumstances had been less fortunate

In Part B of the clinical study complaint form the Sponsor will make the same assessment.

8.6.3 Reporting of device deficiencies

The Investigator shall send the completed clinical study complaint form to the Sponsor.

E-mail for device deficiencies reporting: [contact]

Fax number for device deficiencies reporting: [contact]

^{IV} Inadequacy of device safety refers to properties of the device which could have or have led to an AE.

	Title 43USTT1904 CSP Infraorbital Hollows	Doc id MA-40833
--	---	---------------------------

A device deficiency that led to a SAE and any device deficiency that could have led to a SAE shall be reported to the Sponsor within 24 hours after the Investigator's awareness (for contact information, see section 8.5.7).

If the Investigator or the Sponsor assesses that the device deficiency could have led to a SAE the Sponsor is responsible for reporting the device deficiency to RA and the PI is responsible for reporting it to the IRB.

The deficient study product shall be kept by the study site until the Sponsor has confirmed whether the product shall be returned to Sponsor for further study or if it can be destroyed at the study site.

9. Data Handling and Management

9.1 Data management

Data management based on GCP refers to the activities defined to achieve safe routines to enter clinical data information into a database, efficiently and avoiding errors. The data management routine includes procedures for database set-up and management, data entry and verification, data validation, and documentation of the performed activities including information of discrepancies in the process. The data management process will be described in detail in the data management plan (DMP).

The database, the data entry screens and program will be designed in accordance with the CSP and the CRF template. Data validation will be performed by computerized logical checks and manual review. Drugs and events will be coded in accordance with World Health Organization (WHO) Drug and medical dictionary for regulatory activities (MedDRA) dictionaries as specified in the DMP. Safety data (SAE and if applicable AE of special interest) in the clinical database will be reconciled against the data in the safety database.

When all efforts have been made to ensure that the data recorded in the eCRFs and entered in the database is as correct and complete as possible, the clinical database will be locked. Study data will be transferred to SAS datasets, which thereafter will be write-protected. Statistical analyses will be generated in SAS using data from the locked datasets.

9.2 Electronic case report forms

A 21 Code of Federal Regulations Part 11-compliant electronic data capture application will be used to collect, modify, maintain, archive, retrieve, and transmit study data. An eCRF is required and should be completed electronically for each screen failure as well as enrolled subjects.

The eCRF includes password protection and internal quality checks, such as automatic range checks, to identify data that appear inconsistent, incomplete, or inaccurate. Study data should be entered directly from the source documents, which are to be defined at each site before inclusion of the first subject.

Authorized study site personnel designated by the Investigator should complete data collection. Appropriate training and security measures should be completed with all authorized investigation site personnel prior to the study being initiated and any data being entered into the system for any subject.

The study data is the sole property of the Sponsor and should not be made available in any form to third parties, except for authorized representatives of appropriate RA, without written

	Title 43USTT1904 CSP Infraorbital Hollows	Doc id MA-40833
--	---	---------------------------

permission from the Sponsor. At the end of the study, electronic data are kept at the Sponsor and a copy (provided by the vendor) at the study site as part of the Investigator file.

Any delegation of collection of data should be specified in a signature and delegation log.

9.2.1 Data entry

All data shall be entered in English. The eCRFs should always reflect the latest observations on the subjects participating in the study. Therefore, the eCRFs shall be completed as soon as possible during or after the subject's visit. The subject's identity must always remain confidential, i.e. the name and address of the subjects must not be registered in the eCRFs or in the database. The Investigator must verify that all data entries in the eCRFs are accurate and correct. If some assessments are not done, or if certain information is not available, not applicable or unknown, the Investigator shall indicate this in the eCRF. The Investigator shall electronically sign off the study data. By signing, the Investigator takes responsibility for the accuracy, completeness, and legibility of the data reported to the Sponsor in the eCRF.

9.2.2 The query process

The monitor shall review the eCRFs and evaluate them for completeness and consistency. Each eCRF shall be compared with the respective source documents to ensure that there are no discrepancies between critical data. All entries, corrections, and alterations shall be made by the PI or his/her authorized designee. The monitor cannot enter data in the eCRFs. Once study data have been submitted to the central server via the eCRF, corrections to the data fields will be audit trailed, meaning that the reason for change, the name of the person who made the change, together with time and date will be logged. Roles and rights of the site personnel responsible for entering study data into the eCRF shall be determined in advance. If discrepant data is detected during review of the data, either by the Sponsor or by its representatives, the responsible data manager or monitor shall raise a query in the electronic data capture application. The query shall state the question or data to be changed and shall be resolved in the system by the PI or his/her authorized designee. The appropriate study site personnel shall answer the queries in the eCRF. This will be audit trailed by the electronic data capture application meaning that the name of study site personnel, time, and date is logged.

9.2.3 User identification

Electronic CRF records will be automatically appended with the identification of the creator, by means of their unique UserID. Specified records shall be electronically signed by the Investigator to document his/her review of the data and acknowledgement that the data are accurate. This will be facilitated by means of the Investigator's unique UserID and password; date and time stamps will be added automatically at time of electronic signature. If an entry in an eCRF requires change, the correction shall be made in accordance with the relevant software procedures.

9.2.4 Audit trail

All changes will be fully recorded in a protected audit trail and a reason for the change shall be stated. Once all data have been entered, verified, and validated, the database will be locked.

9.3 **Source documents**

Source documents are all documents used by the Investigator or hospital that relate to the subject's medical history, that verifies the existence of the subject, the inclusion and exclusion

	Title 43USTT1904 CSP Infraorbital Hollows	Doc id MA-40833
--	---	---------------------------

criteria, and all records covering the subject's participation in the study. They include laboratory notes, memoranda, material dispensing records, subject files, etc.

The Investigator is responsible for maintaining source documents. These should be made available for inspection by the monitor at each monitoring visit. The Investigator must submit a completed eCRF for each subject for whom signed informed consent has been collected. All supportive documentation submitted with the eCRF, such as laboratory or hospital records, should be clearly identified with the CTN and subject number. Any personal information, including name, should be removed or rendered illegible to preserve individual confidentiality.

9.4 Record keeping and access to source data

The Investigator/Institution should permit study-related monitoring, audits, IRB review, and RA inspections and should provide direct access to the source data/medical record including the identity of all participating subjects (sufficient information to link records, i.e. eCRF, medical records, original signed informed consent forms and detailed records of study product accountability). The records should be retained by the Investigator as required by local legislation and international guidelines. Any transfer of responsibility for storage of the records should be documented and the Sponsor should be informed in writing.

The Sponsor should verify that each subject has consented in writing to direct access to the original medical record/source data (by the use of written subject information and signed informed consent). The data recorded in the eCRFs will be checked for consistency with the source documents/medical record by the monitor during monitoring (source data verification; SDV). In order to be able to perform SDV, information about each subject's participation in the study has to be detailed in the medical record.

9.5 Document and data retention

All records pertaining to the conduct of the study, including signed eCRFs, informed consent forms, study product accountability records, source documents, and other study documentation must be retained for as long as is specified in the CTA. Measures should be taken to prevent accidental or premature destruction of these documents (e.g. protection against damage and unauthorized access, preferably by storage in a fire-proof cabinet).

It is the Investigator's responsibility to inform the Sponsor in writing if the Investigator file is moved or if the responsibility for the documents is transferred to someone else.

10. Statistical Methods

10.1 General

A comprehensive Statistical Analysis Plan (SAP) with detailed description of all statistical analyses will be developed before database lock.

All study data will be listed in subject data listings.

All statistical analyses, including summary tables and data listings, will be performed using SAS. Confidence intervals (CIs) will be two-tailed and constructed at a confidence level of 95%. Statistical tests will be performed at a significance level of 5%, and p-values will be two-sided, unless otherwise specified.

Continuous endpoints will be summarised using descriptive statistics, e.g. number of subjects (n), mean, median, standard deviation, minimum and maximum values. Categorical endpoints

	Title 43USTT1904 CSP Infraorbital Hollows	Doc id MA-40833
--	---	---------------------------

will be presented in frequency tables with number and percentage of observations for each level.

10.2 Analysis populations

The following populations will be defined:

- **Modified Intention-to-treat (mITT)** Includes all subjects who are randomized and will be analyzed according to the randomization scheme; subjects with a GIHS month 3 assessment via a remote visit will be excluded from the mITT.
- **Intention-to-treat (ITT)** Includes all subjects who are randomized and will be analyzed according to the randomization scheme
- **Per protocol (PP)** Includes all subjects in ITT who complete 3 months after baseline visit without any deviations considered to have substantial impact on the primary effectiveness
- **Safety** Includes all subjects who were treated with *Restylane-L* or randomized to the control group, and will be analyzed according to as-treated principle

The mITT will be used for the primary effectiveness analysis. All secondary effectiveness endpoints will be analyzed based on the ITT population, ^{CCI}

Safety analysis is performed based on the safety population set.

The disposition of subjects will be presented in tables and/or figures as appropriate. The number of screened, treated, completed, and withdrawn subjects will be presented, as well as number of subjects in each analysis population set.

10.3 Demographics, baseline assessments, and subject characteristics

Demographic endpoints, baseline assessments, and subject characteristics will be presented based on the ITT analysis set using descriptive statistics by treatment, as appropriate.

10.4 Effectiveness analysis

10.4.1 Primary effectiveness analysis:

Responder rate based on the GIHS as assessed live by the Blinded Evaluator at month 3 after baseline will be the primary effectiveness endpoint. A responder will be defined as a subject with at least 1 point improvement from baseline on both sides of the face concurrently. For a significant result, the two-sided p-value of the comparison of responder rates between the treated and untreated subjects at month 3, using the Cochran-Mantel-Haenszel (CMH) test stratified by injection tool, needs to be smaller than 0.05.

The null hypothesis will be that there is no relationship between responder rate and treatment group (i.e. the responder rate is the same in both groups). The alternative hypothesis will be that there is a relationship between responder rate and treatment group (i.e. the responder rate is different in the two groups).

	Title 43USTT1904 CSP Infraorbital Hollows	Doc id MA-40833
--	---	---------------------------

The estimates of the responder rate in each treatment group will be presented as well as the difference in responder rates. Corresponding confidence intervals for responder rates and the difference in responder rates along with the p-value for the difference will also be presented.

CCI

10.4.2 Secondary effectiveness analysis:

Responder rates (defined as at least 1 point improvement from baseline on both sides of the face concurrently) based on the GIHS as assessed by the Blinded Evaluator at month 6, 9, and 12 after baseline and at 3 and 6 months after optional treatment will be analyzed in the same way as the primary effectiveness endpoint. No correction for multiplicity will be done; p-values obtained for any endpoint other than the primary will only be provided for ease of interpretation of the results.

All other secondary effectiveness analyses will be done descriptively as appropriate.

10.5 **Safety analysis**

Number and percentage of subjects reporting each pre-defined, expected, post-treatment symptoms, as collected in the 28 days diary, will be presented in total and by maximum severity. Number of days with the event will be presented by treatment group and category: 1, 2-7, 8-13, and 14-28.

All AEs will be coded according to MedDRA and summarized by system organ class (SOC), preferred term (PT) and treatment.

A summary of all AEs will be provided, which will include:

- number of subjects with at least one AE and number of events (in total as well as serious AEs)
- number of subjects with at least one related AE and number of events (in total as well as serious AEs)
- number of subjects with at least one mild, moderate and severe AE and number of events (in total as well as serious AEs)
- number of subjects with at least one unrelated AE and number of events (in total as well as serious AEs)
- number of subjects who did not have an AE

The number of subjects with AEs related to study product or injection procedure as well as the number of events will be summarized by SOC, PT and maximum severity. In addition, for related AEs the number of days to onset and the duration of event will be summarized by SOC and PT using mean, SD, min, max and median. Action taken for related AEs will also be summarized. Serious AEs will be listed. AEs with onset >21 days after most recent treatment will be listed.

Non-related AEs will be summarized by SOC, PT and intensity.

To evaluate consistency of AEs across different subgroups, AEs will also be summarized by subgroups defined as described below.

Safety analysis will be descriptive only.

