At the month 12 visit, the no-treatment comparator subjects will be offered an optional *Restylane-L* treatment. The subjects who received *Restylane-L* at the baseline visit will also be offered an optional additional treatment if optimal aesthetic improvement is not maintained (as determined by the Treating Investigator and subject). For subject receiving optional treatment at month 12 the effectiveness and safety data will be collected for another 6 months. A subject will be involved in the study for up to 19 months including 30 days screening and 6 months follow-up after optional treatment at month 12. The study visits are illustrated in Figure 1.

Effective

[figure not shown]
Version: 10.0

GALDERMA <small>EST. 1981</small>	Title 43USTT1904 CSP Infraorbital Hollows	Doc id MA-40833
---	---	---------------------------

Effective date: 2021-12-15 20:29

Effective

Version: 10.0

	Title 43USTT1904 CSP Infraorbital Hollows	Doc id MA-40833
--	---	---------------------------

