4.7.13 Visit 8c: Follow up visit 1 month (+7 days) after optional treatment

This visit should only be conducted for subjects who received a treatment at Visit 8.

- Interview subject regarding any concomitant therapies and record subject's weight.
- Interview subject and evaluate any AEs, and post-treatment AEs by Treating Investigator that have occurred since the last visit.
- Collect and review Subject Diary:
 - Review diary entries for completeness and legibility.
 - If the subject handwrites entries on the diary pages, review these entries with the subject and clarify as needed. Record all clarifications on the subject's source documents and record the Diary data into the eCRF.
- GAIS assessment – Treating Investigator and Subject
- Obtain photographs
- Schedule Visit 8d, 3 months (\pm 7 days) after optional treatment (Visit 8).

4.7.14 Visit 8d: Follow up visit 3 months (\pm 7 days) after optional treatment

This visit should only be conducted for subjects who received a treatment at Visit 8.

- Interview subject regarding any concomitant therapies and record subject's weight.
- Interview subject and evaluate any AEs that have occurred since the last visit.

Effective

Version: 10.0

	Title 43USTT1904 CSP Infraorbital Hollows	Doc id MA-40833
--	---	---------------------------

Effective date: 2021-12-15 20:29

- Assessments to be performed:
 - GIHS – Blinded Evaluator
 - GAIS – Treating Investigator and Subject

CCI

- Obtain photographs
- Schedule Visit 8e, 6 months (+ 7 days) after optional treatment (Visit 8).

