7.2 Galderma Infraorbital Hollows Scale (GIHS)

The GIHS is a 4 point scale for assessment of Infraorbital Hollows (Appendix 2). Each score in the GIHS is exemplified by Photographic images of the scale. The blinded evaluator and treating investigator will perform live assessment of the subject's left and right Infraorbital Hollow separately.

	Title 43USTT1904 CSP Infraorbital Hollows	Doc id MA-40833
--	---	---------------------------

The blinded evaluator will perform GIHS assessments at:

- screening and baseline
- 3, 6, 9 and 12 months after randomization
- 3 and 6 months after optional treatment. The evaluator is considered unblinded as these assessments are performed for all subjects receiving the optional treatment.

The treating investigator will perform GIHS assessment at:

- screening and baseline
- 1 and 12 months after randomization

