### 9 Appendix F. Effectiveness Estimands

Endpoints	Attributes									
	Population	Endpoints	Treatments	Intercurrent Events	Statistical Summary					
Primary	mITT Population; includes all randomized subjects that did not have a remote month 3 GIHS assessment ITT Population; includes all randomized subjects PP Population	Responder rate based on the Blinded Evaluators' live assessment of the Galderma Infraorbital Hollows Scale (GIHS), at 3 months after baseline.	Restylane-L vs. Control	Subjects that don't have a Month 3 GIHS response, due to missed visit, missed procedure, or discontinuation prior to visit, Subject has a prohibited treatment/procedure performed prior to Month 3; Subject has an unstable medical history affecting the IOH area	Number and difference in proportion (n, %) of subjects					
Secondary 1	ITT Population	Responder rate based on the Blinded Evaluators' live assessment of the GIHS, at 6, 9, and 12 months after baseline and at 3 and 6 months after optional treatment.	Restylane-L vs. Control	Subjects that don't have a GIHS response at a respective visit, due to missed visit, missed procedure, or discontinuation prior to visit	Number and difference in proportion (n, %) of subjects					
Secondary 2	ITT Population	Proportion of subjects having at least "Improved" on the Global Aesthetic Improvement Scale (GAIS), as assessed live by the Subject and Treating Investigator separately at all follow-up visits after baseline.	Restylane-L vs. Control	Subjects that don't have a GAIS response at a respective visit, due to missed visit, missed procedure, or discontinuation prior to visit	Number and proportion (n, %) of subjects					
ICCI										

17:26

									Print date:	2022-08-17
	G	A L D E R M A	43USTT1	904 Statistic	al analysis pla	n - Tear Troug	h	Doc id MA-42205		
Endpoints		Attributes								
		Population		Endpoints		Treatments	Intercurrent Events		Statistical Summary	
CCI										

Print date: 2022-08-17 17:26

43USTT1904 Statistical analysis plan - Tear Trough

MA-42205

Doc id

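### Protocol 10.4.2 and the synopsis extend the treated-versus-untreated test to two visits where every assessed subject has been injected, and SAP Appendix F still lists a difference there despite signs that the SAP intends description only

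*Protocol*

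**What the plan says.** **The method carried over.** Protocol 10.4.1 bases the primary analysis on the "comparison of responder rates between the treated and untreated subjects at month 3", using a CMH test stratified by injection tool. It reports responder rates, their difference, confidence intervals and a p-value.

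**Where it is carried to.** Protocol 10.4.2 states that Blinded Evaluator GIHS responder rates at Months 6, 9 and 12 and "at 3 and 6 months after optional treatment will be analyzed in the same way as the primary effectiveness endpoint". The Statistical Methods part of the synopsis says the same. Protocol 10.2 adds: "All secondary effectiveness endpoints will be analyzed based on the ITT population", a population analyzed by randomized arm.

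**Who is seen at the later visits.** The 3- and 6-month ratings after optional treatment come from Visits 8d and 8e. Protocol 4.7.14 and 4.7.15 both carry the restriction: "This visit should only be conducted for subjects who received a treatment at Visit 8". On those ratings, Protocol 7.2 says: "The evaluator is considered unblinded as these assessments are performed for all subjects receiving the optional treatment".

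**How subjects reach those visits.** Under Protocol 4.1, at Month 12 "the no-treatment comparator subjects will be offered an optional" treatment. Subjects first given Restylane-L "will also be offered an optional additional treatment if optimal aesthetic improvement is not maintained".

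**What the SAP says.**
- Appendix F, Secondary 1, puts all five time points in one row, sets Restylane-L against control, and gives the summary as "Number and difference in proportion (n, %) of subjects".
- Section 1.4.2(i) attaches a difference to Months 6, 9 and 12 but only proportions to the two later time points, while still wording them as versus no treatment.
- Section 2.4.4.1 applies the CMH test by visit with no visible exception, and leaves open whether p-values will be produced.
- The version 3.0 entry in section 2.9 records that the two later time points become descriptive.
- Section 2.8 says that Protocol Version 10.0 now matches the SAP.

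**The concern.** The secondary objective is to compare Restylane-L with no treatment. At 3 and 6 months after optional treatment nobody assessed is untreated, so the method named in the protocol has no comparator. It can still be computed if the columns are filled by randomized arm, and that is the risk: the program would run and print a difference and a p-value under a Restylane-L versus control heading. A difference near zero could be taken as loss of effect, when it may only mean that both groups had been injected. A large difference would mix repeat versus first injection with the different routes by which the two groups came to be treated.

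At stake is the reading of one secondary table, not the trial's main conclusion.

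**Working it through.** The visible text gives no figure for this comparison, so there is nothing to reproduce. The check sets the visit design beside the analysis rule.

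**1. Count the time points (Protocol 3.1.2, 4.7.10, 4.7.14, 4.7.15).**

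| Secondary GIHS time points | Number | Who is rated | Untreated subjects possible? |
|---|---|---|---|
| Months 6, 9, 12 after baseline | 3 | Both randomized arms; the Month 12 rating precedes optional treatment | Yes, up to about 47 |
| 3 and 6 months after optional treatment | 2 | Only subjects injected at Visit 8 | None |

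Total 3 + 2 = 5, so the rule lacks an untreated comparator at 2 of 5.

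**2. Fill the columns by randomized arm (Protocol 10.2, 10.7, 10.11).** The planned arms are 146 + 136 = 282 for Restylane-L and 47 for no treatment, 329 in all. Secondary endpoints use observed cases. At these two time points the no-treatment column can therefore hold at most about 47 subjects, all injected. The Restylane-L column can hold at most about 282, all injected again. Actual numbers depend on uptake, which the documents do not give.

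**3. Ask what the contrast would mean.**
- *Selection:* every former control is offered treatment. Restylane-L subjects are offered it only when improvement has not been maintained. Observation at Visits 8d and 8e depends on that offer and its acceptance, so randomization no longer protects the comparison.
- *Exposure:* a re-treated Restylane-L subject has had the initial session, possibly a Month 1 touch-up, and the Month 12 session, that is two or three sessions. A former control has had one by Month 12.
- *Reference point:* response is improvement from the study baseline, so any remaining effect of earlier injections counts for the re-treated group only.
- *Rating:* the evaluator is considered unblinded.

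The contrast is thus re-treated versus first-treated, in groups selected by different rules. It estimates no effect against no treatment.

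**4. Compare the places that govern these two time points.**

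| Place | Test | Difference |
|---|---|---|
| Protocol synopsis and 10.4.2 | CMH, as for the primary | Yes |
| SAP Appendix F, Secondary 1 | None named | Yes |
| SAP 1.4.2(i) | None named | No, proportions only |
| SAP 2.4.4.1 (visible text) | CMH by visit, no exception | Yes, by reference to 2.4.3 |
| SAP 2.9, version 3.0 entry | Descriptive | Not called for |

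The change-history entry serves here only as evidence of intent. Its difference from other text is not itself counted as an error.

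**The case against.** The strongest reply is that the sponsor has already dealt with this. Protocol 10.1 leaves detailed analysis to the SAP. SAP version 3.0 was written on Protocol Version 10, its change entry is dated one day after that protocol, and it records the two time points as descriptive. SAP 1.4.2(i) keeps the difference for Months 6, 9 and 12. Appendix F is a summary table that names no test. The opening of SAP 2.4, to which SAP 2.8 sends the reader for changes in analysis, is redacted. Both documents say that these ratings are unblinded, and secondary p-values are unadjusted and offered only as an aid to interpretation.

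Much of this stands. A reader might infer that both documents firmly plan a treated-versus-control test here, or that the SAP forgot an exception. The documents support neither: the SAP leans towards description, and what is redacted cannot be called missing. A reader might also want to say how far the result would mislead, in percentage points or in error rate. No response or uptake rates are given, so any such number would only restate what was assumed.

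The reply does not remove the unredacted sentences in the synopsis and Protocol 10.4.2, or the Appendix F row. No exception elsewhere in the SAP changes those words. On this point the statement in SAP 2.8 that protocol and SAP match does not fit a descriptive intent.

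**Conclusion.** The point holds as a minor inconsistency in the analysis rule. As written, the protocol applies a treated-versus-untreated test, difference and p-value at 2 of 5 secondary GIHS time points with no untreated subjects, and Appendix F keeps the matching difference. The finding rests on visible text and on the visit design, and needs no assumed rates.

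It does not follow that a misleading table will be produced: if the SAP's descriptive intent is carried out, none will be. Nor does it follow that the evidence of effectiveness is weakened. The Month 3 primary analysis and the Month 6, 9 and 12 comparisons keep their untreated comparator and are unaffected.

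**What to change.** In the synopsis, Protocol 10.4.2 and the Appendix F Secondary 1 row, limit the CMH test, difference and p-value to Months 6, 9 and 12. State the same exception in SAP 2.4.4.1 if the redacted part of SAP 2.4 does not already do so.

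For 3 and 6 months after optional treatment, report responder proportions with confidence intervals descriptively by randomized arm. Label the groups *randomized to Restylane-L, re-treated at Month 12* and *randomized to No Treatment, first treated at Month 12*. Mark the ratings as unblinded and make no between-group test. The SAP's existing initial-treatment label (section 2.5.1) would not do alone, because it also covers the baseline injection of the Restylane-L arm.

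The protocol wording needs a small dated amendment with IRB review, and regulatory review if applicable (Protocol 12.3). A lighter route is to edit Appendix F and, where needed, the SAP text, and to record the departure from the protocol in the clinical study report, where Protocol 10.10 and SAP 2.1 already place deviations from the statistical plan. Neither route needs new data or touches the primary analysis.
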